### 2.5.4.1. Immunogenicity Assessments

Immunogenicity assessments will include the following:

- Serum RSV-A neutralizing and RSV-B neutralizing antibody levels
- Serum Anti-HA antibody levels for influenza measured by HAI assay

RSV binding antibody levels may be presented as appropriate.

### 2.5.4.2. Analysis of the Primary Immunogenicity Endpoints

The co-primary endpoints will be analyzed on the PP Set in order to estimate Estimands 1a-3a (refer to [Appendix I](#), Table 9). In addition, this will be supported by estimation of a treatment policy Estimand (Estimands 1b-3b) on the FAS Set, and by a principal stratum Estimand (Estimands 1c and 2c) on the Supportive PP Set.

#### 2.5.4.2.1. Primary Analysis Approach

The co-primary endpoints include the following:

- GMT of serum RSV-A nAbs at Day 29
- SRR of serum RSV-A nAbs at Day 29
- GMT of serum influenza anti-HA Abs for each influenza strain (A/Victoria, A/Cambodia, B/Victoria, B/Phuket) at Day 29

The statistical analyses are:

- For the co-primary endpoints 1) and 3), the GMT ratio (GMR) between coadministered group and mRNA-1345 plus placebo group or between coadministered group and Afluria Quadrivalent plus placebo group will be estimated using an ANCOVA model on the log-transformed tiers at Day 29, with the vaccination group as the fixed variable, log-transformed baseline titers as a fixed covariate, adjusted for randomized age group. The GLSM for each vaccination group and its corresponding 95% CI in a log-transformed scale will be estimated from the model and back-transformed to obtain the estimates in the original scale as an estimate of the GMT and its 95%CI. The GMR will be estimated by the ratio of the GLSMs and the corresponding 2-sided 95% CI to assess the treatment difference. The noninferiority of the GMT will be demonstrated if the LB of the 95% CI of the GMR is  $> 0.667$  based on the noninferiority margin of 1.5.
- For the primary endpoint 2), SRR for RSV-A nAbs at Day 29 will be provided with 2-sided 95% CIs using the Clopper-Pearson method. The SRR difference between coadministered group and mRNA-1345 plus placebo group at Day 29 will be provided with 2-sided 95% CIs using the Miettinen-Nurminen's method. The noninferiority of the SRR will be demonstrated if the LB of the 95% CI of the SRR difference is  $> -10\%$  based on the noninferiority margin of 10%.

The study is considered to meet the primary immunogenicity objective if the noninferiority of the immune response to mRNA-1345 coadministered with Afluria Quadrivalent based all the co-primary endpoints.

The above analysis corresponds to the Primary Immune Estimands 1a-3a as described in [Appendix I](#), Table 9.

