**Table 2: Sample Size Justification for the Co-primary Immunogenicity Endpoints**

Primary Endpoint	Number of Evaluable Participants (with 10% ineligible for Per-protocol Set)	$\alpha$	Standard Deviation	GMR/SRR Assumed	NI Margin	Power
mRNA-1345 Noninferiority (2-sided test)						
Day 29 GMT Coadministration (Group 2) vs. alone (Group 1)	378(Group 1) 540(Group 2)	0.05	1.5	GMR=1	1.5	98%
Day 29 SRR Coadministration (Group 2) vs. alone (Group 1)	378 (Group 1) 540 (Group 2)	0.05		SRR=0.8 in both groups	10%	96%
Afluria Quadrivalent Noninferiority (2-sided test) for Each Influenza Strain						
Day 29 GMT Coadministration (Group 2) vs. alone (Group 3)	540 (Group 2) 540 (Group 3)	0.05	1.5	GMR=1	1.5	99%
Overall power to show noninferiority of the primary immunogenicity endpoints						90%

With 540 participants to be included in PP Set in mRNA-1345 + Afluria Quadrivalent (Group 2) and 378 participants to be included in PP Set in mRNA-1345 + placebo (Group 1):

- There is at least 98% power to demonstrate the noninferiority of the immune response to RSV-A, as measured by GMT of RSV-A nAb in participants receiving mRNA-

1345 plus Afluria Quadrivalent compared with that in mRNA-1345 plus placebo group, at a 2-sided alpha of 0.05, assuming a noninferiority margin of 1.5 and an underlying GMR of 1. The standard deviation of the natural log-transformed level is assumed to be 1.5.

- There is at least 96% power to demonstrate the noninferiority of the immune response, as measured by SRR of RSV-A nAbs at Day 29 in participants receiving mRNA-1345 plus Afluria Quadrivalent compared with that in mRNA-1345 plus placebo group, at a 2-sided alpha of 0.05, assuming an SRR of RSV-A nAbs of 80% in both groups (a true SRR difference is 0), and a noninferiority margin of 10%.

With 540 participants to be included in PP Set in either mRNA-1345 plus Afluria Quadrivalent group (Group 2) or Afluria Quadrivalent plus placebo group (Group 3):

- There is at least 99% power to demonstrate noninferiority of the immune response to each of the 4 influenza strains, as measured by GMT of influenza anti-HA Abs for each strain in participants receiving mRNA-1345 plus Afluria Quadrivalent compared with that in Afluria Quadrivalent plus placebo group, at a 2-sided alpha of 0.05, assuming a noninferiority margin of 1.5 and an underlying GMR of 1. The standard deviation of the natural log-transformed level is assumed to be 1.5.

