#### 2.5.4.2.3. Supportive Analysis

A supportive analysis will be conducted to mitigate the potential power reduction due to the IRT error described in [Section 2.3.4](#). The primary immunogenicity endpoints of GMT and SRR, based on serum RSV-A nAbs at Day 29, will be analyzed on the Supportive PP Set.

The definition of Supportive PP Set can be found in [Section 2.4.3](#). It is estimated that approximately 180 participants in the Per-protocol Immunogenicity Set from mRNA-1345-P301 will be included, along with Group 1 and Group 2 participants in Per-protocol Set from mRNA-1345-P302 to form the Supportive PP Set. The participants from mRNA-1345-P301 and the Group 1 participants from mRNA-1345-P302 will be pooled together and compared with the Group 2 participants from mRNA-1345-P302.

This supportive analysis will be conducted when Part A database is locked and the immunogenicity data for participants in the Supportive PP Set is available. The corresponding Estimand is 1c as described in [Appendix I, Table 9](#). The same definition for the endpoints and the same statistical methods as described in [Section 2.5.4.2.1](#) will be applied in this supportive analysis.

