#### **2.5.5. Multiplicity Adjustment**

[figure not shown]
A sequential/hierarchical testing procedure will be used to control the overall Type 1 error rate at 0.05 (2-sided) over the primary endpoints, key secondary efficacy endpoints, and selected secondary endpoint. The hierarchical order for the hypotheses to be tested is indicated in [Figure 1](#).

The co-primary endpoints will be tested at the planned primary analysis at a 2-sided Type 1 error rate of 0.05. The success criteria of all 6 co-primary endpoints need to be met in order to declare the study a success to achieve noninferiority of coadministration.

The key secondary endpoints will only be tested at the primary analysis at a 2-sided Type 1 error rate of 0.05 when all co-primary endpoints have met success criteria of noninferiority. And the key secondary endpoints will be tested sequentially by GMR of RSV-B nAbs first, SRR of RSV-B nAbs second, then SCR of anti-HA Abs for each influenza strain last.

No further testing will be performed once the sequence/hierarch breaks, that is, further testing stops as soon as an endpoint in the sequence fails to meet success criterion of noninferiority. Analyses of remaining other secondary immune endpoints are not controlled for multiplicity.

**Figure 1** Testing Strategy of Co-primary and Key Secondary Immunogenicity Endpoints

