#### **3.5.4.2.1. Primary Analysis Approach**

The co-primary endpoints include the following:

- 1) GMT of serum RSV-A nAbs at Day 29
- 2) SRR in serum RSV-A nAbs at Day 29
- 3) GMC of serum nAbs for each of the 2 SARS-CoV-2 strains (Wuhan-Hu-1 and B.1.1.529) at Day 29
- 4) SRR in serum nAbs for each of the 2 SARS-CoV-2 strains (Wuhan-Hu-1 and B.1.1.529) at Day 29

The statistical analyses are:

- For the co-primary endpoints 1) and 3), the GMR of RSV-A nAbs or the GMR of nAbs for each of the 2 SARS-CoV-2 strains between vaccination groups will be estimated using an ANCOVA model on the log-transformed titers/concentrations at Day 29, with the vaccination group as the fixed variable, log-transformed baseline titers/concentrations as a fixed covariate, adjusted for randomized age group. The GLSM for each vaccination group and its corresponding 95% CI in a log-transformed scale will be estimated from the model and back-transformed to obtain the estimates in the original scale as an estimate of the GMT or GMC and its 95% CI. The GMR will be estimated by the ratio of the GLSMs

and the corresponding 2-sided 95% CI to assess the treatment difference. The noninferiority of the GMT or GMC will be demonstrated if the LB of the 95% CI of the GMR is  $> 0.667$  based on the noninferiority margin of 1.5.

- For the co-primary endpoints 2) and 4), SRR in RSV-A nAbs or SRR in nAbs for each of the 2 SARS-CoV-2 strains at Day 29 will be provided with 2-sided 95% CIs using the Clopper-Pearson method. The SRR difference between vaccination groups at Day 29 will be provided with 2-sided 95% CIs using the Miettinen-Nurminen's method. The noninferiority of the SRR in RSV-A nAbs at Day 29 will be demonstrated if the LB of the 95% CI of the SRR difference between mRNA-1345 + mRNA-1273.214/ placebo and mRNA-1345 + placebo/ mRNA-1273.214 groups is  $> -10\%$ . The noninferiority of the SRR in nAbs for each of the 2 SARS-CoV-2 strains at Day 29 will be demonstrated if the LB of the 95% CI of the SRR difference between mRNA-1345 + mRNA-1273.214/ placebo and mRNA-1273.214 + placebo/ placebo groups is  $> -10\%$ .

The study is considered to meet the primary immunogenicity objective if the noninferiority of the immune response to mRNA-1345 + mRNA-1273.214/ placebo based all the co-primary endpoints.

The above analysis corresponds to the Primary Immune Estimands 5a-8a as described in [Appendix I](#), Table 11.

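### The SRR and SCR comparisons do not adjust for baseline titer or age group as the GMT/GMC models do; adjusting keeps the randomised comparison and may add zero to a few points of power

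*SAP*

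**What the plan says.** SAP 2.5.4.2.1 treats the Part A co-primaries in two ways. The GMT endpoints use an ANCOVA with "log-transformed baseline titers as a fixed covariate, adjusted for randomized age group". For the RSV-A SRR endpoint, "The SRR difference between coadministered group and mRNA-1345 plus placebo group at Day 29 will be provided with 2-sided 95% CIs" by the Miettinen-Nurminen method, with no covariate.

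SAP 2.5.4.3 repeats this split for RSV-B SRR and for influenza SCR. For the Part B co-primaries, SAP 3.5.4.2.1 states: "The SRR difference between vaccination groups at Day 29 will be provided with 2-sided 95% CIs using the Miettinen-Nurminen's method". SAP 3.5.4.3 does the same for Part B RSV-B SRR. Protocol 2.8.5.1 and 3.8.1.1 and Estimands 2a, 6a and 8a in SAP Appendix I agree.

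Baseline does enter the responder definition (SAP 2.2.1.2 and 2.2.2.1): a rise of at least 4-fold over the participant's own baseline, or a fixed threshold when baseline is below the assay limit.

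The sensitivity analyses (SAP 2.5.4.2.2 and 3.5.4.2.2) change the analysis set and keep the method. On the IRT error, SAP 2.5.4.2.3 says: "A supportive analysis will be conducted to mitigate the potential power reduction due to the IRT error". It pools about 180 participants from study P301 with Group 1 and applies the same methods.

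**The concern.** Baseline titer and age group are collected on everyone, and the GMT/GMC models already use them. If baseline predicts who reaches a 4-fold rise, leaving it out of the SRR comparison gives a wider interval than necessary and lets a chance baseline difference move the estimate.

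The SRR tests have the least room. The plan's own tables give them the lowest co-primary power: 96% against 98% and 99% in Part A, and 97.8% against 99% in Part B. All six co-primaries in a part must succeed. The IRT error then cut Group 1 from 420 to about 250 and weakened the Part A RSV comparisons further.

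The Supportive PP Set adds a separate reason. Its P301 participants are not randomised against Group 2 and are all 60 or older, while Part A enrols from 50. The GMT comparison there adjusts for baseline and age; the SRR comparison adjusts for neither.

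**Working it through.** **Inputs from the documents.** Two-sided alpha is 0.05, SRR is 80% in both groups and the margin is 10% (SAP 2.3.3 and 2.5.5). Planned evaluable numbers are 378 and 540 in Part A and 504 per group in Part B. PP loss is 10%. About 250 were randomised to Group 1 (SAP 2.3.4). The SD of ln titer is 1.5.

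**Not in the documents.** There is no baseline SD and no baseline-to-Day 29 correlation. The only within-person correlation, 0.65 in SAP 4.3.3, is between two post-dose titers.

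**Step 1: reproduce the planned power.** SE = sqrt(0.16 × (1/n1 + 1/n2)); power = Φ(0.10/SE − 1.96).

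- Part A: SE = sqrt(0.16 × (1/378 + 1/540)) = 0.02682, so power = Φ(1.77) = 96.1%. The SAP says: "There is at least 96% power to demonstrate the noninferiority of the immune response, as measured by SRR of RSV-A nAbs at Day 29". Exact enumeration of the Miettinen-Nurminen test gives 96.7%.
- Part B: SE = sqrt(0.16 × 2/504) = 0.02520, so power = Φ(2.01) = 97.8%, as stated. Exact: 97.7%.

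**Step 2: after the IRT error.** Group 1 is 250 × 0.9 = 225. Group 2, keeping 1620 in total, is (1620 − 250)/2 × 0.9 ≈ 617.

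- SRR: SE = sqrt(0.16 × (1/225 + 1/617)) = 0.03115, so power = Φ(1.25) = **89.4%**. Exact Miettinen-Nurminen: **92.5%**.
- RSV-A GMT, same numbers: Φ(ln 1.5/(1.5 × sqrt(1/225 + 1/617)) − 1.96) = Φ(1.51) = 93.5%, against 98.1% planned.
- Reading 5:14:14 as about 700 randomised to Group 2 (630 evaluable) changes little: SRR power is 89.6%, or 92.7% exact.

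**Step 3: how much could baseline explain?** Let X be baseline and Y Day 29 ln titer, with SD(Y) = 1.5. Seroresponse depends on Y − X. In a bivariate normal model, baseline predicts the change only so far as the slope of Y on X, ρ × 1.5/SD(X), differs from 1. R² is the share of the responder variable's variance explained by baseline at SRR 80%. Adjusted power is Φ(0.10/(SE × sqrt(1 − R²)) − 1.96).

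| Baseline SD | Correlation | R² | Part A RSV-A SRR, 225 vs 617 | Part B SRR, 504 vs 504 |
|---|---|---|---|---|
| unadjusted | – | – | 89.4% | 97.8% |
| 1.0 | 0.65 | 0.000 | 89.4% | 97.8% |
| 1.2 | 0.80 | 0.000 | 89.4% | 97.8% |
| 1.0 | 0.50 | 0.018 | 90.0% | 98.0% |
| 1.5 | 0.80 | 0.051 | 90.9% | 98.3% |
| 1.5 | 0.65 | 0.091 | 92.0% | 98.6% |
| 1.5 | 0.50 | 0.13 | 93.2% | 98.9% |

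These rows are illustrations, not bounds. At baseline SD 1.5 and correlation 0.3, for example, R² is 0.19.

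**Step 4: does the adjusted estimator behave?** A logistic model with group and baseline, standardised to a marginal risk difference, was simulated at 225 versus 630 (4,000 replicates, crude Wald interval as comparator). Power went from 91.2% to 93.7% at SD 1.5 and correlation 0.5. At SD 1.0 and correlation 0.65 it went from 90.9% to 90.6%, which is no gain. One-sided type I error at the margin was 2.45% adjusted and 2.48% crude in the first setting.

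**The case against.** Four points count against pressing this hard.

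- **The premise is assumed.** A reader might infer that baseline strongly predicts a 4-fold rise and that precision is being given away for free. No section says so. Because the endpoint is already a ratio to own baseline, the gain vanishes when the slope of Day 29 on baseline is near 1. At baseline SD 1.0 and correlation 0.8 the direction reverses, so that high-baseline participants respond more often. Assuming equal SDs rules these cases out. This stands.
- **The starting power is better than 89.4%.** That figure is a normal approximation. The planned Miettinen-Nurminen test has 92.5%, so the choice of approximation moves the answer by 3.1 points, almost as much as the largest tabulated gain. This stands.
- **The P301 pooling replaces nothing.** A reader might infer that the sponsor swaps the randomised test for a non-randomised one. SAP 2.5.4.2 and 2.5.4.2.3 make the pooled analysis supportive only; the confirmatory test remains Group 2 versus Group 1 on the PP Set.
- **Changing the primary method has a cost.** Protocol 2.8 and 3.8 call for an amendment when methods for primary or secondary objectives change after study start. Part A's EDC database was already locked when the IRT error surfaced.

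These limit the size of the point and the form of the fix. They do not explain why no adjusted SRR or SCR analysis appears anywhere, even as sensitivity.

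**Conclusion.** The point holds as a modest, optional improvement. The SRR and SCR comparisons omit two covariates that the GMT/GMC models use, and nothing in the plan fills the gap. It would be too strong to say that the plan ignores baseline titer, since baseline defines every responder; it is the between-group comparison that does not adjust. Nor is there a bias or error-rate fault: the unadjusted test of randomised groups is valid.

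Across the tabulated assumptions, baseline explains about 0% to 13% of the responder variance. That is worth zero to a few points for the Part A RSV-A SRR test (89.4% to between 89.4% and 93.2% by normal approximation) and about 1 point or less per Part B SRR test. These figures rest on an assumed baseline SD and correlation, a bivariate normal model, SRR 80% in both groups and 10% PP loss. In the Supportive PP Set the case for adjustment rests on the age difference and the lack of randomisation, and does not depend on the power gain.

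**What to change.** In SAP 2.5.4.2.1, 2.5.4.3, 3.5.4.2.1 and 3.5.4.3, prespecify for each SRR and SCR endpoint a standardised (marginal) risk difference from a logistic model with vaccination group, log baseline titer and randomised age group. Keep the -10% margin; the quantity estimated is still the marginal difference in proportions. Add the same analysis for SRR on the Supportive PP Set in SAP 2.5.4.2.3, and state how P301 participants are assigned to the age categories.

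Status should depend on blinding. In a part that is still blinded, and with Protocol 2.8.5.1 or 3.8.1.1 aligned, make the adjusted difference primary and report the crude Miettinen-Nurminen interval as sensitivity. Otherwise leave the planned test primary and add the adjusted difference as a sensitivity analysis.

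The cost is one more table, an entry in SAP Section 5 with protocol alignment, and, where the adjusted analysis is primary, an interval that cannot be recomputed from raw counts alone. The SAP already accepts a model-based SRR difference in Part C (SAP 4.5.4.3), so the approach is not new to the study.

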#### **2.3.4. Randomization**

The randomization will be in a blinded manner using a centralized IRT, in accordance with pre-generated randomization schedules.

The study will enroll approximately 1620 medically stable adults  $\geq$  50 years of age. Participants will be randomized with a ratio of 7:10:10 to receive either 1) mRNA-1345 + placebo (Group 1, 420 participants); 2) mRNA-1345 + Afluria Quadrivalent (Group 2, 600 participants); or 3) Afluria Quadrivalent + placebo (Group 3, 600 participants). Randomization will be stratified by age (50 to 59 years, 60 to 74 years, and  $\geq$  75 years). The study will target enrollment of approximately 20% of participants 50 to 59 years of age. Randomization details is described in [Section 2.3.1](#).

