#### 2.5.4.3. Analysis of the Key Secondary Immunogenicity Endpoints

The key secondary endpoints include the following:

- 1) GMT of serum RSV-B nAbs at Day 29
- 2) SRR in serum RSV-B nAbs at Day 29
- 3) SCR in serum influenza anti-HA Abs for each influenza strain (A/Victoria, A/Cambodia, B/Victoria, B/Phuket) at Day 29

The statistical analyses are:

- GMT of RSV-B nAbs at Day 29 will be analyzed using the same ANCOVA model as for RSV-A nAbs at Day 29. The GLSM for each vaccination group and GMR between coadministered group and mRNA-1345 plus placebo group and associated 95% CIs will be estimated from the ANCOVA model.
- SRR in RSV-B nAbs at Day 29 will be provided with 2-sided 95% CIs using the Clopper-Pearson method. The SRR difference between coadministered group and mRNA-1345 plus placebo group at Day 29 will be provided with 2-sided 95% CIs using the Miettinen-Nurminen's method.
- SCR in anti-HA Abs for each influenza strain at Days 29 will be provided with 2-sided 95% CIs using the Clopper-Pearson method. The SCR difference between coadministered

group and Afluria Quadrivalent plus placebo group at Day 29 will be provided with 2-sided 95% CIs using the Miettinen-Nurminen's method.

The key secondary endpoints of GMT and SRR, based on serum RSV-B nAbs at Day 29, will also be analyzed on the Supportive PP Set.

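### The SRR and SCR differences ignore the age strata used for randomisation; this leaves a conditional bias risk for RSV SRR in Part A after Group 1 closed early, and only a small inconsistency elsewhere

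*SAP*

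**What the plan says.** SAP 2.3.4 states: "Randomization will be stratified by age", in three bands (50 to 59, 60 to 74, 75 and over). Part B uses the same bands (SAP 3.3.1).

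The GMT co-primaries in SAP 2.5.4.2.1 use an ANCOVA with "log-transformed baseline titers as a fixed covariate, adjusted for randomized age group". SAP 3.5.4.2.1 does the same for the Part B GMT and GMC.

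The binary endpoints are handled without age:

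- Part A co-primary RSV-A SRR: the difference "at Day 29 will be provided with 2-sided 95% CIs using the Miettinen-Nurminen's method" (SAP 2.5.4.2.1).
- Part B co-primary SRRs: "The SRR difference between vaccination groups at Day 29 will be provided with 2-sided 95% CIs using the Miettinen-Nurminen's method" (SAP 3.5.4.2.1).
- Part A key secondary SCR: the difference between the coadministered "group and Afluria Quadrivalent plus placebo group at Day 29 will be provided with 2-sided 95% CIs using the Miettinen-Nurminen's method" (SAP 2.5.4.3). RSV-B SRR is treated the same way there and in SAP 3.5.4.3.

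Protocol 2.8.5.1 and 3.8.1.1 and the estimand tables in SAP Appendix I agree, so this is a settled choice. No planned analysis adjusts SRR or SCR for age. The FAS analysis (SAP 2.5.4.2.2) and the Supportive PP Set analysis (SAP 2.5.4.2.3) reuse the primary methods, and age-subgroup immunogenicity analyses are optional (SAP 2.5.4.6).

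**The concern.** All six co-primaries must succeed in each part, yet age is in the model for some and absent for others, and the plan gives no reason. While stratified randomisation holds, this costs only a little precision.

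Part A is different. SAP 2.3.4 reports that an IRT error closed Group 1 on 25 May 2022, when 959 participants had been randomised, and that Group 1 stayed closed until after enrolment ended on 9 June. Groups 2 and 3 continued. Group 1 is therefore compared with a Group 2 that was partly recruited later, and the strata no longer force the same age mix in the two groups. The GMT model would adjust for a difference between age bands; the SRR test would not. If SRR falls with age, an older Group 2 pushes the RSV-A and RSV-B SRR tests towards failure, and a younger Group 2 pushes them towards a false claim of noninferiority. The SAP treats the error as a loss of power and does not discuss balance in the PP Set.

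**Working it through.** **Inputs from the documents.** SAP 2.3.3 (Table 2 and its text) gives "With 540 participants to be included in PP Set in mRNA-1345 + Afluria Quadrivalent (Group 2) and 378 participants" in Group 1, and the power is computed "at a 2-sided alpha of 0.05, assuming an SRR of RSV-A nAbs of 80% in both groups" with a 10-point margin and 10% of participants outside the PP Set. SAP 2.3.4 gives planned allocation 7:10:10, closure at 959, about 250 in Group 1, and an actual ratio of about 5:14:14.

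**Inputs assumed, because the documents do not give them.** SRR by age band, the split between 60 to 74 and 75 and over, and any change in age mix after closure.

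**1. Reproduce the plan's figure.** Power = Φ(0.10/SE − 1.96), with SE = √[0.8 × 0.2 × (1/378 + 1/540)] = 0.0268. This gives 96.1%, against 96% stated. The exact unstratified Miettinen-Nurminen rule gives 96.7%.

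**2. After the IRT error.**
- Group 1: 959 × 7/27 ≈ 249, matching the stated 250.
- Group 2: 959 × 10/27 ≈ 355 before closure and (1620 − 959)/2 ≈ 330 after, about 685 in all. Late share 330/685 ≈ 48%.
- PP sizes: 0.9 × 250 = 225 and 0.9 × 685 ≈ 616.
- SE = √[0.16 × (1/225 + 1/616)] ≈ 0.0312. The interval half-width is 1.96 × 0.0312 ≈ 6.1 points.
- RSV-A SRR power: 89.4% by normal approximation, 92.5% by exact Miettinen-Nurminen. RSV-A GMT power falls from 98.1% to 93.4%.

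**3. Balanced ages.** With an age mix of 20/55/25%, the share of SRR variance lying between age bands is 0.7% for SRRs of 85/80/75%, 2.7% for 90/80/70% and 6.1% for 95/80/65%. Even the last makes the crude interval only about 3% wider. In simulations of the Miettinen-Nurminen rule, stratifying gains at most 0.7 power points in Part A and at most 0.2 in Part B.

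**4. Age drift in Part A.** Suppose the late 48% of Group 2 has a fraction d moved from 50 to 59 into 75 and over. Then

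shift in the crude difference = −0.48 × d × (SRR youngest − SRR oldest).

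The smallest case below is 0.48 × 0.05 × 0.10 = 0.24 points and the largest is 0.48 × 0.15 × 0.20 = 1.44 points. Simulated power (200,000 replicates, 225 vs 616, mix 20/55/25%, no true within-age difference):

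| Drift | SRR by age | Shift (points) | Crude | Stratified |
|---|---|---|---|---|
| 5 | 85/80/75 | −0.2 | 90.9% | 92.2% |
| 5 | 90/80/70 | −0.5 | 89.2% | 92.3% |
| 10 | 85/80/75 | −0.5 | 89.6% | 92.1% |
| 10 | 90/80/70 | −1.0 | 85.8% | 92.1% |
| 15 | 85/80/75 | −0.7 | 87.8% | 91.7% |
| 15 | 90/80/70 | −1.4 | 81.6% | 91.8% |

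With the drift reversed (Group 2 younger) and a true within-age difference of −10 points, one-sided error for drifts of 10 and 15 points is 3.5 to 6.6% crude and 2.6 to 2.7% stratified.

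A separate simulation at 225 vs 617 with a 10-point drift and gradients from 85/80/75% to 90/80/60% gives crude error of 3.7 to 6.2% against about 2.7% stratified. In the other direction, crude power is 0.80 to 0.90 against 0.91 to 0.93. The steepest gradient shifts the difference by 0.48 × 0.10 × 0.30 = 1.44 points.

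**The case against.** The strongest reply is that an unstratified Miettinen-Nurminen interval is valid when ages are balanced, that it is the protocol's stated method, and that the plan's power reproduces without stratification. That stands. It leaves only consistency and slight efficiency for Part B, which has equal groups and no IRT error, and for influenza SCR, where Groups 2 and 3 both stayed open.

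Next, the Part A bias needs two facts that the documents do not show: a change in age mix after participant 959, and an SRR that varies with age. That also stands; the effect is conditional.

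A reader might infer more from the early closure, in three ways:

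- *That a 10-point age imbalance between Groups 1 and 2 is a natural case.* Only 48% of Group 2 enrolled late, so this needs late enrolees to differ from early ones by 10/0.48 ≈ 21 points, within about 15 days. Nothing in the documents suggests that.
- *That RSV-A SRR alone decides Part A.* It is one of six co-primaries. It has the lowest power after the error, but RSV-A GMT (93.4%) is close to it.
- *That the GMT model removes any imbalance.* It adjusts for baseline titer and three age bands, not for calendar time.

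A large imbalance would also be seen, because age group is tabulated by vaccination group (SAP 2.5.2.1 and 2.5.2.2). It would not be adjusted for, and the tables are not split by enrolment period.

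Finally, replacing a co-primary method is more than a wording change. Protocol 2.8 and 3.8 call for an amendment when methods for primary or secondary objectives change, and the Part A EDC database was already locked when the error came to light, although before unblinding and before immunogenicity data were available (SAP 2.3.4). This limits the remedy but does not remove the gap.

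**Conclusion.** The inconsistency is real in both parts and both documents. Its cost under balanced ages is very small: under 1 power point in Part A and about 0.2 or less in Part B.

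For the Part A comparison of Groups 1 and 2 (RSV-A and RSV-B SRR), age balance is no longer guaranteed by design, and the crude difference is unprotected. Over the cases worked above it would shift by roughly 0.2 to 1.4 points, against a 10-point margin and a 6.1-point half-width. That could tip a borderline result but would not by itself reverse a clear one. Stratifying costs no power when ages are balanced and holds error and power close to their intended values when they are not.

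The documents do not support saying that the SRR result is biased. They leave the possibility open, and the sponsor can check it directly from the age mix by group and period.

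**What to change.** - In SAP 2.5.4.2.1 and 2.5.4.3, and in Estimands 2a and 2b, specify a Miettinen-Nurminen SRR difference stratified by randomised age group for Group 1 versus Group 2. Keep the -10% margin and report the crude interval alongside.
- For consistency, apply the same to SCR in 2.5.4.3 and to the SRR differences in 3.5.4.2.1 and 3.5.4.3.
- Align protocol 2.8.5.1 and 3.8.1.1 through the amendment route in protocol 2.8 and 3.8.
- If Part A is already unblinded, keep the crude interval as the decision rule and add the stratified one as a labelled sensitivity analysis.
- Tabulate age mix by group before and after 25 May 2022.

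The cost is document changes and minor programming, with no new data. There are two downsides. The estimate becomes an age-weighted common difference. Stratifying by age also does not remove other differences between early and late enrolees.
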